5.5.2 Randomisation and Blinding

This study will not involve randomisation. Due to the titration aspect of the preceding double-blinded study (SAG/0211PFC-1131), bottles will not specifically identify whether they contain lubiprostone 12 or 24 mcg so as to maintain the prior blind. Dose assignment will be based on the dose they were receiving at the time of rolling over from the preceding, double-blind study (SAG/0211PFC-1131) into this safety extension study for those subjects who were randomised to receive lubiprostone during the preceding study. For subjects who received placebo during the preceding study (as identified via IXRS), assignment of dose by the IXRS will be based on subject body weight at the time of rollover to this extension study. Dose assignment will only be known in subjects who were at least 50 kg in weight at the time of randomisation in the preceding study (SAG/0211PFC-1131). All dose assignments will be handled by the IXRS and will continue to maintain blinding with respect to the treatment assignment in the preceding trial.

Most study personnel will remain blinded to doses assigned to subjects weighing less than 50 kg until the clinical database has been locked. To allow for the execution of clinical trial-related services, the following individuals will be unblinded during the study:

- External RTSM vendor
- Sponsor Quality Assurance representative
- Sponsor Pharmacovigilance representative
- External clinical supply distribution vendor

- External third party unblinded biostatistician (e.g., DSMB statistician)
- DSMB members
- Bioanalytical laboratory and third-party pharmacokinetic analyst
- Sponsor Drug Supply Management representative

Emergency unblinding by the Investigator of a subject's assigned treatment is addressed in [Section 4.6](#) of this protocol.

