8.1 Determination of Sample Size

The sample size goal is based on the expected attrition that would occur and the remaining number of safety evaluable subjects at each timeframe during the study.

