8.2 Datasets Analysed

Two analysis populations, Safety population and the modified Intent-to-Treat (mITT) population and these will be defined as follows:

- **The Safety population** will consist of all enrolled subjects who take at least one dose of study medication.
- **The mITT population** will include all enrolled subjects who take at least one dose of study medication and have at least one treatment period diary entry.

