8.5.2 Adverse Events

The original terms used in the eCRF by Investigators to identify AEs will be coded to MedDRA® system organ class and preferred terms. Adverse events will be summarized in terms of incidence per dose group and overall. The incidence of an AE is defined as the number of subjects who experienced at least one episode during the study. Adverse event incidence rates will be summarized by system organ class (SOC) and preferred term (as determined by the coding).

Whatever the level of classification, if a subject experiences multiple episodes of an event within the given time reference, then the event is only counted once. Further, for summaries by severity or causality, the most severe event is chosen for a subject if that subject experiences multiple episodes of the same event.

In this study, faecal impaction and bone fractures will be captured as AEs. The events of faecal impaction will be used for the analysis of the faecal impaction frequency during the study (see [Section 8.6.2.6](#)).

AEs with onset dates after administration of the first dose of study medication or prior to the last day of treatment + 7 days will be considered treatment-emergent. Events with completely or partially missing onset dates will be included in the tabulations, unless the available partial date information clearly indicates that the event happened outside of the treatment period.

P-values from Fisher's exact test or chi-square test will be presented in the AE summary tables. The test will be performed to compare incidence rates at the SOC and "At Least One Event" level between the two treatment groups.

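### Section 8.5.2 states only crude AE incidence: under drop-out this understates 36-week on-treatment risk for events that accrue over time, and it biases the dose comparison only if drop-out differs by dose

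*Combined protocol and SAP*

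**What the plan says.** Section 2.1 makes safety the primary objective, over 36 weeks of treatment. Section 8.1 bases the sample size on "the expected attrition that would occur and the remaining number of safety evaluable subjects at each timeframe during the study", without giving an attrition rate or a target count.

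Section 8.5.2 defines the AE measure: "The incidence of an AE is defined as the number of subjects who experienced at least one episode during the study". On repeat events it adds that "if a subject experiences multiple episodes of an event within the given time reference, then the event is only counted once"; no time reference other than the study itself is defined. It gives results by dose group and overall. It also says "P-values from Fisher's exact test or chi-square test will be presented in the AE summary tables", comparing the two groups at system organ class and any-event level. An event counts as treatment-emergent up to 7 days after the last day of treatment.

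Section 8.5.2 names no denominator. The natural candidate is the Safety population of Section 8.2, which "will consist of all enrolled subjects who take at least one dose of study medication".

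Exposure is summarised separately in Section 8.4 and is not linked to AEs. Event timing appears only in the listings of deaths, serious AEs and adverse terminations (Section 8.5.1). One event captured as an AE, faecal impaction, has a monthly analysis, but as an efficacy endpoint (Section 8.6.2.5). Section 8 leaves further detail to a SAP to be finalised before database lock.

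**The concern.** A subject who leaves at week 6 has a treatment-emergent window of about 7 weeks but counts as fully in the denominator as one who stays 36 weeks. A crude proportion therefore mixes the rate at which events occur with the time subjects were observed. Three things are at stake.

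- **Level of risk.** The study exists to describe long-term safety. A reader will tend to take the tabulated percentage as the risk over 36 weeks of treatment, which is too low for events that keep occurring.
- **Time course.** A single proportion cannot show whether events cluster early or accumulate. Section 8.1 refers to evaluable subjects at successive timeframes, but Section 8.5.2 uses none of them.
- **Comparisons.** P-values are attached to the crude proportions by dose group. Section 4.5 lists AE and lack of efficacy among the withdrawal reasons, and both could vary with dose. The Synopsis also says the safety data will be considered together with 100 younger subjects from another study. Crude proportions are hard to compare across groups with different follow-up.

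**Working it through.** **Inputs from the documents:** 36 weeks of treatment; about 415 subjects; a subject-count definition of incidence; two dose groups. No attrition rate, AE rate, precision target or dose-group size is given, so 415 cannot be reproduced.

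**Assumptions:** true 36-week risk p of 5% to 40%; drop-out d by week 36 of 0% to 40%; constant event hazard; drop-out independent of the event; an all-treated denominator; groups of 208 and 207; two-sided 5% tests (Section 8.6.1 states that level for efficacy only). The 7-day tail after last treatment is ignored.

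**1. Crude incidence under drop-out, two models.**

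Model A, exponential drop-out: l = -ln(1-p)/36 and m = -ln(1-d)/36 per week; crude = l/(l+m) × (1 - exp(-36(l+m))).

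Model B, drop-out spread evenly over 36 weeks: with L = -ln(1-p), crude = (1-d)p + d(1 - p/L).

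For p = 0.20, L = 0.2231 and 1 - p/L = 0.1037. At d = 0.20, Model B gives 0.80 × 0.20 + 0.20 × 0.1037 = 0.1807. At d = 0.30 it gives 0.1400 + 0.0311 = 0.1711. At d = 0.40 it gives 0.1200 + 0.0415 = 0.1615.

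| Drop-out | Model A, p = 20% | Model B, p = 20% | Relative shortfall for p = 5% to 40% (A; B) |
|---|---|---|---|
| 20% | 18.0% | 18.1% | 9.5-10.3%; 9.2-9.9% |
| 30% | 16.9% | 17.1% | 14.6-15.8%; 13.7-14.9% |
| 40% | 15.8% | 16.1% | 20.0-21.5%; 18.3-19.8% |

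In counts, with 415 subjects, p = 10% and d = 30%, Model A expects 35.0 subjects with an event instead of 41.5.

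**2. Early-onset events.** Put the whole 10% risk in week 1 and keep 30% drop-out by week 36. The weekly hazards are l = 0.1054 and m = 0.0099, so crude = 0.1054/0.1153 × (1 - exp(-0.1153)) = 9.95%, a loss of about 0.5% relative.

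**3. Dose comparison with equal drop-out.** With equal hazards and 30% drop-out in both groups, the rejection rate stays at 0.050. With true risks of 10% and 20%, the crude figures are 8.4% and 16.9%. The risk ratio barely moves (2.01 against 2.00), and the risk difference shrinks from 10 to 8.5 points.

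**4. Dose comparison with unequal drop-out and equal hazards, p = 20%.**

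- 20% against 30%: ratio 0.1693/0.1800 = 0.94 (A) or 0.1711/0.1807 = 0.95 (B). False rejection under Model A is 0.054 to 0.072 for p from 10% to 40%.
- 20% against 40%: ratio 0.1581/0.1800 = 0.88 (A) or 0.1615/0.1807 = 0.89 (B). False rejection under Model B is about 0.08.
- 10% against 40%, an extreme case: ratio 0.1581/0.1902 = 0.83 (A). False rejection is 0.091 to 0.258 for p from 10% to 40%.

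**5. What person-time recovers.** With p = 20%, l = 0.2231/36 = 0.00620 per week. First events divided by time at risk give 0.00620 × 52.18 × 100 = 32.3 per 100 person-years at every drop-out level from 0% to 40%. This converts back to 1 - exp(-36 × 0.00620) = 20.0%.

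**The case against.** The strongest reply is that the crude proportion is a valid estimate of something useful: the probability of an on-treatment AE before stopping, in subjects managed as these were. AEs that cause withdrawal are still counted. This stands. The shortfall concerns only the risk had everyone stayed on treatment for 36 weeks, and it nearly vanishes for early-onset events.

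A reader might infer that drop-out as such distorts the dose comparison. It does not. Step 3 shows that equal drop-out leaves the test level and the risk ratio essentially intact. The documents do not say that drop-out will differ by dose; the withdrawal reasons only make it plausible. At a modest imbalance (20% against 30%) the inflation of false rejections is small.

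A reader might also infer that no exposure-adjusted AE analysis is planned anywhere. That goes too far. Section 8 refers to a SAP whose text is not in the document reviewed, and the all-treated denominator is itself an inference. What can be said is that Section 8.5.2 fixes the incidence definition and the test, and neither takes account of time.

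Finally, exposure adjustment does not make the dose comparison causal. Section 5.5.2 says "This study will not involve randomisation"; dose follows prior dose or, for former placebo subjects, body weight. Person-time rates and Kaplan-Meier estimates also need non-informative drop-out, which withdrawal for AE or lack of efficacy puts in doubt. Both limits stand and should be stated with the results. The separate exposure summary, the event listings and the DSMB are useful but do not give risk over time.

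**Conclusion.** The point holds in a limited form. As written, Section 8.5.2 reports crude AE incidence alone, in a study built to describe long-term safety and sized in expectation of attrition. For events that accrue over time, the tabulated figure would be about 10%, 15% and 20% (relative) below the 36-week on-treatment risk at 20%, 30% and 40% drop-out. Two drop-out models agree closely on this, and it varies little with the true risk. The sizes rest on constant hazard, independent drop-out and assumed rates. The actual size cannot be derived from the documents.

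Bias in the dose comparison is conditional on drop-out that differs by dose. This is a worthwhile, inexpensive improvement to the plan; it does not show that the planned table is invalid. The final SAP should be checked before the analysis is called absent.

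**What to change.** In Section 8.5.2, keep crude incidence, name its denominator, and add by dose group and overall:

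- for any treatment-emergent AE, each system organ class and the common preferred terms, first events per 100 person-years, with time to first event or to last dose + 7 days, whichever comes first, as the denominator;
- for the same terms, incidence by 12-week interval with the number at risk at the start of each interval;
- for any treatment-emergent AE only, Kaplan-Meier cumulative incidence at Weeks 12, 24 and 36.

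The interval table is needed as well as the rate, because a single rate per person-time cannot show early clustering. State that these estimates assume non-informative drop-out, and that dose comparisons remain confounded by body weight and prior dose. Carry the same definitions into the SAP before database lock.

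The cost is a few extra tables from onset dates (Section 7.1.5) and exposure data (Section 8.4) already collected. Reported risks may look slightly less favourable.

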3.1 Study Procedure Overview

A detailed description of the procedures to be performed is outlined in [Section 6, study procedures](#). The schedule of events is outlined in tabular format in the Protocol Synopsis section.

There will be four distinct visits or periods during the study:

- **Enrolment Visit (Visit 9; Day 1):** This visit is considered study Day 1 and the visit takes place on the first day of study medication administration and will coincide with Visit 7 of the preceding study SAG/0211PFC-1131.
- **Interim Treatment Clinic Examinations (Visits 10, 12, 14; Weeks 1, 12, 24) and End-of-Treatment Visit (Week 36):** A clinic visit will occur on Study Days 8 (± 2 days), 85 (± 3 days), 169 (± 3 days) and 253 (± 3 days). Clinical assessments will be performed to evaluate the safety of study treatment.
- **Interim Telephone Assessments (Visits 11, 13, and 15; Weeks 4, 16, and 28):** A telephone assessment will be performed by site personnel at Study Days 29 (± 3 days), 113 (± 3 days), and 197 (± 3 days). This assessment will be performed to evaluate the compliance of the subject with the study medication and electronic diary and to identify any adverse events (AEs) or changes in concomitant medications.
- **Follow-up Visit (Visit 17; Week 40 [Day 281 + 3 days]):** A follow-up clinic visit will occur to review any ongoing or new onset of AEs, record any changes in concomitant medications. The subject's overall condition will be assessed; and blood and urine will be collected for laboratory analyses. This will conclude the subject's involvement in the study.

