5.5 Supply and Dosing

Each bottle of study medication will contain 64 capsules, sufficient for 28 days plus a 4-day overage in the event that any capsules are lost, accidentally destroyed, or there is a delay in the completion of the scheduled clinic visit. Each treatment day should consist of two (2) doses of study medication, one (1) capsule per dose in the morning and in the evening. If a dose is missed, the subject should take the missing dose as soon as possible, but should not “double up” doses, i.e., take 2 doses at one meal.

The subject and his/her parent/legal guardian will be instructed to administer study medication with meals and at least 8 ounces (240 mL) of fluid. All doses should be taken at least 5 hours apart. The parent/legal guardian should record the actual time the dose was taken in the electronic diary. If the dose was missed entirely, the parent/legal guardian should indicate the omission in the electronic diary as instructed. The study medication will be handled by authorized personnel and dispensed under the supervision of the Investigator or designated site personnel.

Each subject will receive one 64-capsule bottle of study medication at the Enrolment Visit (Day 1), and three bottles each at Visits 10, 12, and 14. The first dose of study medication will be administered in the clinic at the Enrolment Visit and the Study Coordinator will record this first dose.

Subjects should return the used bottle of study medication at each clinic visit for collection by site for drug accountability. If the study medication is not returned, the bottle of all unused study medication should be returned to the site at the subsequent office visit. The subject will be instructed to take the study medication only from the newly dispensed bottle. The last dose of study medication in this study will be taken on the day of End of Treatment (Visit 16).

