Physical Examination – A complete physical examination of the subject will be performed by appropriate site personnel. Physical examination findings should correlate with the subject's medical history and current diagnosis.

Abbreviated Physical Examination – An abbreviated physical examination of the subjects will be performed by appropriate site personnel. This examination reviews only those body systems where there has been a change in health or there is new finding to report.

Laboratory Tests – Urine and blood samples will be collected and sent to a central laboratory for analysis (see [Section 6.3](#) for details). Age-appropriate normative clinical laboratory values, based on the clinical laboratory's paediatric ranges, will be used to determine abnormal laboratory values for this study.

Pregnancy Test – All female subjects of childbearing potential will have a urine pregnancy test performed at all clinic visits. Childbearing potential will be defined as any female subject who has reported first menses.

Pharmacokinetic Evaluations – Sample collections for the determination of lubiprostone and metabolite M3 concentrations will be performed in all subjects.

Bone Growth Assessments – For those subjects who were aged 6 to 9 or 14 to 17 at the time of enrolment into the SAG/0211PFC-1131 study, and who were qualified to participate and enrolled in the DXA substudy, BMD and BMC measurement using DXA will be performed at Month 9 (Visit 16). All subjects who withdraw from the study after Visit 12 (Month 3) should complete the final visit of the treatment period (Visit 16) and therefore have a final DXA assessment performed. This will only be required for subjects that were originally part of the DXA subgroup. Analysis of scans will be performed by a central reader.

Any subject demonstrating a decline in 4% in BMD at any skeletal site from Screening to End of Treatment should additionally undergo a follow-up DXA assessment 6 to 12 months later.

Adverse Events – AEs will be reported by the subject from the time of informed consent through the end of the follow-up period. AEs will be followed by the Investigator as determined by Sponsor or designee. Further details on AE reporting are provided in [Section 7](#).

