6.1.4.1 Follow-up (Clinical Assessment) – Visit 17 (Week 40/Day 281 +3 days)

The follow-up visit is scheduled to assess all AEs since the end of treatment to determine if resolution has occurred or update the ongoing status of these events. Also, any new events should be recorded. A review of the subject's concomitant therapy should be made to determine if any changes have been made.

At this visit, the following procedures will be performed:

- Review and update concomitant therapy;
- Review and record any new AEs and follow-up on any ongoing AEs;
- Vital signs including height and weight;
- Abbreviated physical examination;
- Collect blood and urine samples for clinical laboratory analysis (including a urine pregnancy test if applicable). A total of about 5.5 mL of blood will be collected for clinical laboratory analysis; and
- Collect electronic diary.

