7. ADVERSE AND SERIOUS ADVERSE EVENTS

As defined in ICH GCP Guideline E6,¹⁴ an AE is any untoward medical occurrence in a clinical investigation subject administered a pharmaceutical product and which does not necessarily have a causal relationship with this treatment. An AE can therefore be any unfavorable and unintended sign (including an abnormal laboratory finding), symptom, disease or exacerbation of a pre-existing condition temporally associated with the use of a medicinal (investigation) product, whether or not related to the medicinal product. For this study, all safety information will be collected from the time of informed consent and any untoward medical occurrence after enrolment will be defined as an AE. Adverse events that are reported after initiation of study medication will be defined as treatment-emergent AEs.

In this study, faecal impaction and bone fractures will be captured as AEs. The events of faecal impaction will be used for the analysis of the faecal impaction frequency during the study (see [Section 8.6.2.5](#)).

Each AE requires a complete and thorough description including date of onset, duration, intensity/severity, its relationship to the study drug and any corrective actions taken. Each AE should also be categorized as “serious” or “non-serious”.

Timely, accurate, and complete reporting and analysis of safety information from the clinical study are crucial for the protection of subjects and are mandated by regulatory agencies worldwide.

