7.2 Recording and Reporting of Adverse Events

All AEs will be recorded in the source document and applicable eCRF(s) from the time the informed consent is signed until the end of study. AEs occurring prior to the first dose of study drug will be considered non-treatment emergent. Any ongoing AEs will be followed until they are resolved, stabilized, or until 30 days after the end of treatment exposure. The Investigator shall notify the Sponsor at any time when an SAE is believed to be related to the administration of study medication, even after the end of the study. At any time during the study, those events meeting the definition of an Immediately Reportable Event (IRE) must be recorded on source document, IRE Reporting Form, and applicable eCRF(s), and then reported to Sponsor or designee using the IRE Reporting Form as specified in [Section 7.2.1](#).

All AEs that have not resolved by the end of the study, or that have not resolved upon discontinuation of the subject's participation in the study, must be followed until either:

- the event resolves;
- the event stabilizes;
- the event returns to baseline, if a baseline value is available;
- the event can be attributed to other than the study medication, or to other than study conduct;
- the Investigator does not anticipate any further improvement or worsening of the event.

All AEs, regardless of seriousness, severity or presumed relationship to study medication, must be recorded using medical terminology in the source document and in the eCRF. Whenever possible, diagnoses should be given when signs and symptoms are due to a common etiology (e.g., cough, runny nose, sneezing, sore throat, and head congestion should be reported as "upper respiratory infection"). Investigators must record on the source document and eCRF their opinion concerning the relationship of the AE to study therapy and the severity of the event. All measures required for AE management must be recorded in the source document and reported according to Sponsor instructions.

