8.5.3 Clinical Laboratory Tests

For clinical laboratory data, mean changes from pre-treatment to post-treatment visits will be summarized using descriptive statistics. Cross-tabulations analysis will be performed for laboratory parameters with reference normal ranges. The laboratory data will be categorized as low, within, and above the reference normal ranges. The summary tables will tabulate the number and percentage of subjects with pre-treatment values below/within/above the normal reference range versus minimum/maximum/final post-treatment values below/within/above the normal reference range. Normal reference ranges will also be provided in the summary display. Laboratory parameters that are not specified in the protocol will not be included in the analysis, but they will be provided in the individual subject listings.

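### Section 8.5.2 joins the two limits of the treatment-emergent window with *or*, so the rule excludes no dated adverse event and disagrees with Sections 7 and 7.2

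*Combined protocol and SAP*

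**What the plan says.** The protocol defines treatment-emergent adverse events (AEs) in three places.

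- Section 8.5.2, the analysis section, takes "AEs with onset dates after administration of the first dose of study medication or prior to the last day of treatment + 7 days".
- Section 7 says: "Adverse events that are reported after initiation of study medication will be defined as treatment-emergent AEs".
- Section 7.2 says: "AEs occurring prior to the first dose of study drug will be considered non-treatment emergent".

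Section 8.5.2 defines incidence by subjects with one or more episodes while on study. It adds p-values comparing the two treatment groups at system organ class and any-event level, but does not say whether these tables are restricted to treatment-emergent AEs. Events with missing or partial onset dates are included unless the known part places them clearly outside the treatment period. Section 6.1.3 ends that period at the last dose.

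On collection, Section 6.1.1 states: "AEs will be reported by the subject from the time of informed consent through the end of the follow-up period". Section 6.1.4 sets follow-up at 4 weeks after the final dose.

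For laboratory data, Section 8.5.3 cross-tabulates pre-treatment values against "minimum/maximum/final post-treatment values below/within/above the normal reference range", with no on-treatment cut-off. The Schedule of Evaluations and Section 6.1.4.1 include blood and urine sampling at Visit 17.

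**The concern.** A treatment-emergent window needs a lower and an upper limit that both apply. Joined by *or*, they cancel each other: an event before the first dose passes the upper limit, and an event late in follow-up passes the lower one. The other two sections do not repair this, because they differ from Section 8.5.2 and from each other.

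Safety is the primary objective (Section 2.1), and AE incidence is the first safety endpoint listed (Section 2.2.1). Two programmers working from this protocol could produce different AE tables, each able to cite a section in support.

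The laboratory tables have a related gap. If the last sample collected supplies the final value, a completer's shift is measured after four weeks without study drug. Section 5.7.1 also lifts the ban on other constipation medicines one week after the End-of-Treatment Visit. An abnormality present at Week 36 and gone by Week 40 would appear as normal.

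**Working it through.** No sample size, power or alpha figure bears on this point. The check is one of logic, followed by a count of days.

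**Inputs**
- First dose F = Day 1. Section 3.1 on Visit 9: "This visit is considered study Day 1 and the visit takes place on the first day of study medication administration".
- Last dose L = Day 253, the day of Visit 16 (Sections 5.5 and 6.1.3.4; window +3 days).
- End of follow-up = L + 28 = Day 281 (Sections 6.1.4 and 6.1.4.1; window +3 days).

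**Step 1: the literal rule.** An AE with onset day t counts if t > F or t < L + 7.
- If t ≤ F, then t ≤ L < L + 7, so the second condition holds.
- If t ≥ L + 7, then t > F, so the first condition holds.
- Anything between meets both.

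No dated AE is excluded. A grid search over first-dose, last-dose and onset days found 0 exceptions.

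**Step 2: the definitions side by side, for a completer**

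| Event | Section 7 | Section 7.2 | 8.5.2 as written | 8.5.2 with *and* |
|---|---|---|---|---|
| Onset and report before first dose | no (implied) | no | yes | no |
| Onset before first dose, reported after it | yes | no | yes | no |
| Onset after first dose, up to Day 259 | yes | not excluded | yes | yes |
| Onset on Day 260 (L + 7) | yes | not excluded | yes | depends on whether day +7 is included |
| Onset Days 261 to 281 | yes | not excluded | yes | no |

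Replacing *or* with *and* settles the conflict with Section 7.2. Section 7 still disagrees in the second row (report against onset) and the last row (no upper limit).

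**Step 3: size of the remaining conflict, in days**
- Day +7 included: 281 − 260 = 21 days; 21/281 = 7.5%.
- Day +7 excluded: 281 − 259 = 22 days; 22/281 = 7.8%.
- Visits 16 and 17 both 3 days late (L = 256, end Day 284), day +7 excluded: 22/284 = 7.7%.

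For early withdrawals the share is 21/(L + 28) or 22/(L + 28), assuming follow-up runs 28 days from the last dose. Two illustrative stopping days:
- L = 28: 21/56 = 37.5% or 22/56 = 39.3%.
- L = 8: 21/36 = 58.3% or 22/36 = 61.1%.

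**Step 4: time before the first dose.** AE collection starts at consent. Consent is a Visit 9 procedure, and the first dose is given at the same visit. This interval should be short.

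**Step 5: laboratory timing.** Samples are drawn at Visits 10, 12, 14, 16 and 17. On the planned days Visit 17 falls 281 − 253 = 28 days after the last dose. With the visit windows it is 25 days (281 − 256) to 31 days (284 − 253), always well beyond 7.

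**The case against.** The strongest reply is that *or* is a slip and the intent is plain. Section 7.2 excludes pre-dose events, and the missing-date sentence in Section 8.5.2 makes sense only if some events fall outside the window. The Amendment 3 rationale for Section 5.7.1 also describes treatment-emergent events as usually reaching 7 days past discontinuation. This stands as evidence of intent. It does not settle Section 7, which has no upper limit and goes by report.

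Two further points reduce the consequences. Section 7.1.5 records the start date and time of each event as well as when it was reported, so any definition can be applied later without new data. Section 8 defers detail to a SAP to be finalised before database lock; no separate SAP text was available here, so the final rule may already be corrected. Both stand, but neither makes Section 8.5.2 right.

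On the laboratory data, Section 8.5.3 never says that the final value includes Visit 17. That is the literal reading, not a stated rule. The section at least needs to define the term.

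Three stronger readings are tempting and are not supported:
- *That the main safety tables are shown to be wrong.* Section 8.5.2 counts episodes on study and does not tie the tables to the treatment-emergent rule, so their counts may not depend on it.
- *That AEs from study SAG/0211PFC-1131 still open at Visit 9 are counted twice.* Section 6.1.2 asks sites to follow ongoing AEs, but nothing says such an event is re-entered as a new AE in this study. No AE table pooling the two studies is described.
- *That 7.5% or 37.5% of AEs are misclassified.* These are shares of days. The documents give no AE rates.

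**Conclusion.** Wrong as written; should be fixed. The treatment-emergent rule in Section 8.5.2 excludes no dated AE, contradicts Section 7.2 and differs from Section 7. If *and* is taken as intended, Section 7 and Section 8.5.2 still disagree over 21 to 22 of 281 planned days per completer and over a larger share for early withdrawals. This assumes that visits fall on their planned days and that follow-up lasts 28 days from the last dose. The effect before the first dose is probably small. How many AEs would change class, and whether any reported rate would move, cannot be computed.

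The laboratory point is smaller: Section 8.5.3 lacks an on-treatment limit, and under its literal wording a completer's final value is an off-drug value.

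**What to change.** 1. Use one definition in Sections 7, 7.2 and 8.5.2: onset (not report) at or after the first dose in this study **and** no later than last dose + 7 days, with day +7 included. Use the recorded onset time to class events on Day 1.
2. Apply the same window to events with missing or partial onset dates, in place of a treatment period that ends at the last dose.
3. State that the AE incidence tables and their p-values use treatment-emergent AEs. Tabulate AEs with later onset separately as post-treatment.
4. In Section 8.5.3, limit the minimum, maximum and final shift values to samples taken up to last dose + 7 days, and show Visit 17 as a separate off-treatment column.

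The cost is protocol and SAP wording before database lock, plus the separate AE and laboratory displays. No visit, sample or data field is added. Counts in the main AE tables may become somewhat smaller, with the removed events still visible in the post-treatment table.
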